#### 8.2 SETTING

EUHASS is a pharmacovigilance program dedicated to monitoring the safety of treatments for people with inherited bleeding disorders in Europe. It is investigator-led, coordinated by the University of Sheffield, and its activities are overseen by an independent Steering Committee. The 96 participating centers in 30 countries report information on all the patients they treat, thus preventing selection bias. Since its initiation in 2008, EUHASS has been used by pharmaceutical companies to conduct post-approval authorization studies.

#### 8.3 VARIABLES

Variables are captured using information from standard patient management. No additional evaluations are done as a consequence of participation in the EUHASS registry or as a consequence of this study.

# 8.3.1 Primary Safety Variables

The primary variables for this study are as follows:

- TEs
- TMA events
- Anaphylaxis events
- Exposure to emicizumab

Adverse events collected in EUHASS are not collected according to MedDRA Classification. Most events are collected according to pre-specified lists; however, free-text fields are also available for each event. For the purpose of this protocol, whenever possible the adverse events are coded by Roche according to MedDRA Preferred Term (PT) level using the most current MedDRA version. A listing of the events reported by EUHASS with the corresponding MedDRA attribution assigned will be provided.

# 8.3.2 Secondary Variables

The secondary variables for this study are as follows:

- Transfusion transmitted infections
- New inhibitors (antibodies against the coagulation factor)
- Allergic and other acute reactions, with the exception of anaphylaxis
- New malignancy diagnosis
- Death

- Unexpected poor efficacy
- Other adverse events possibly related to concentrate
- Exposure to emicizumab, without replacement factor products in the same calendar year
- Exposure to both aPCC and emicizumab in the same calendar year
- Exposure to both rFVIIa and emicizumab in the same calendar year
- Exposure to both FVIII and emicizumab in the same calendar year

# 8.4 DATA SOURCE(S)

Data collection through the EUHASS system is described in detail in the EUHASS Working Protocol (see Appendix 1) and Data Entry Site User Manual (see Appendix 2). Briefly, the reporting is done electronically through a Web-based system. Participating centers are asked to provide information on selected adverse events quarterly by completing a Web-based adverse event reporting form and also have the option of reporting an event at the time of its occurrence. If they report occurrence of an event, additional questions are asked as described in Section 7.1.

In addition, centers also provide annual information on the number of patients treated with each type of coagulation product allowing for calculation of incidence proportion of each adverse event collected across the entire registry by product. Additionally, EUHASS will also collect aggregate information on the number of patients who use emicizumab and aPCC, emicizumab and rFVIIa, and emicizumab and FVIII, thus allowing for calculation of incidence rates of TE and TMA among patients exposed to emicizumab concomitantly with each of these drugs.

#### 8.5 STUDY SIZE

The sample size will depend on the approval and uptake of emicizumab in the countries with centers participating in the EUHASS registry. As per last data available at the time of this protocol amendment (1 January 2021- 31 December 2021), 1,319 patients were treated with emicizumab alone, 71 patients were treated with emicizumab and NovoSeven, 490 patients were treated with emicizumab and other FVIII (other than Obizur), and 3 patients were treated with emicizumab and Factor Eight inhibitor bypassing activity (FEIBA).

Table 3 provides exact incidence proportions and 95% confidence intervals that apply to each of the primary safety variables (TMA, TE, anaphylaxis), for a range of numbers of events observed.

Table 3 Incidence Proportions and Corresponding 95% Cls for Each Primary Safety Variable Based on 680 Patients Receiving Emicizumab, Assuming Different Numbers of Events

Number of Patients with at least One Adverse Event Observed	Corresponding Proportion (95% Two-Sided CI Exact Binomial)
0	0% (0% – 0.05%)
1	0.15% (0%; 0.82%)
5	0.74% (0.24%; 1.71%)
10	1.5% (0.71%; 2.69%)
20	2.9% (1.81%; 4.51%)
50	7.3% (5.51%; 9.58%)

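### Table 3 is computed on an unexplained N of 680, although the same section reports at least 1,809 patients exposed in 2021; its zero-event limit is wrong at either N

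*Protocol*

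**What the plan says.** Protocol Section 8.5 sets no target number; it makes the size depend on approval and uptake in the participating countries. It then gives the most recent exposure figures: "As per last data available at the time of this protocol amendment (1 January 2021- 31 December 2021"). In that year "1,319 patients were treated with emicizumab alone", "71 patients were treated with emicizumab and NovoSeven" and "490 patients were treated with emicizumab and other FVIII (other than Obizur"), and 3 received emicizumab with FEIBA.

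The next paragraph introduces Table 3 as giving "exact incidence proportions and 95% confidence intervals that apply to each of the primary safety variables (TMA, TE, anaphylaxis"). The caption states the basis: "Based on 680 Patients Receiving Emicizumab, Assuming Different Numbers of Events". The column head gives the method: "Corresponding Proportion (95% Two-Sided CI Exact Binomial").

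Three other places fix the relevant denominator:
- Section 7.2: the primary objective covers all exposed patients, whether or not they also used factor products.
- Section 8.7: data are analysed annually for 2018-2024, and proportions may be calculated each year for all exposed patients.
- Section 8.3.2: exposure to emicizumab alone means no replacement factor in the same calendar year.

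**The concern.** The table is presented as applying to the primary safety variables, but its denominator matches none of the exposure counts printed above it. The number 680 is about half of the emicizumab-alone group by itself. Nothing in the protocol says where it comes from, which year it describes, or that it is only an illustration.

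Table 3 is the protocol's only quantitative statement of precision. The events are rare, so the low-count rows matter most, and the zero-event row in particular tells a reader what risk could be excluded if no case were seen. If that table does not fit the current population, a reader or regulator takes the wrong bound from it.

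**Working it through.** **Inputs.** N = 680, exact binomial, two-sided 95% (Table 3). 2021 counts of 1,319, 71, 490 and 3 (Section 8.5).

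**Formulae (Clopper-Pearson), x events in n patients.** Lower limit = Beta quantile(0.025; x, n-x+1). Upper limit = Beta quantile(0.975; x+1, n-x). For x = 0 the lower limit is 0 and the upper limit is 1 - 0.025^(1/n).

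**Step 1: bound the 2021 total.** The alone group excludes same-year factor users, so it is taken as disjoint from the co-exposed groups. How far the co-exposed groups overlap one another is not stated.
- Full overlap (rFVIIa and aPCC users all within the FVIII group): 1,319 + 490 = 1,809.
- No overlap: 1,319 + 71 + 490 + 3 = 1,883.
- Ratios to the table's N: 1,809/680 = 2.66; 1,883/680 = 2.77; the alone group, 1,319/680 = 1.94.

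The FVIII count leaves out Obizur. Emicizumab-plus-Obizur patients not counted in another group would add to the total, so 1,883 is not a strict maximum. The minimum of 1,809 stands.

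**Step 2: reproduce the table, then recompute it.** Entries are % (95% CI).

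| Events | Printed | Recomputed, N = 680 | N = 1,809 | N = 1,883 |
|---|---|---|---|---|
| 0 | 0 (0; 0.05) | 0 (0; 0.541) | 0 (0; 0.204) | 0 (0; 0.196) |
| 1 | 0.15 (0; 0.82) | 0.147 (0.004; 0.817) | 0.055 (0.001; 0.308) | 0.053 (0.001; 0.296) |
| 5 | 0.74 (0.24; 1.71) | 0.735 (0.239; 1.708) | 0.276 (0.090; 0.644) | 0.266 (0.086; 0.619) |
| 10 | 1.5 (0.71; 2.69) | 1.471 (0.707; 2.688) | 0.553 (0.265; 1.014) | 0.531 (0.255; 0.974) |
| 20 | 2.9 (1.81; 4.51) | 2.941 (1.806; 4.506) | 1.106 (0.677; 1.702) | 1.062 (0.650; 1.636) |
| 50 | 7.3 (5.51; 9.58) | 7.353 (5.506; 9.579) | 2.764 (2.058; 3.628) | 2.655 (1.977; 3.486) |

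All five rows with events reproduce at 680, apart from a trivial rounding of 7.353 to 7.3. So 680 is the basis actually used and not a misprint in the caption. The unknown overlap moves the recomputed figures by at most about 0.15 percentage points (row 50, upper limit: 3.628 - 3.486 = 0.142).

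**Step 3: the zero-event row.** At 680, 1 - 0.025^(1/680) = 0.541%. A one-sided 95% limit, 1 - 0.05^(1/680), would be 0.440%. Neither is 0.05%. Solving for n at an upper limit of 0.05% gives ln(0.025)/ln(0.9995), about 7,376 patients, or ln(0.05)/ln(0.9995), about 5,990 on the one-sided variant. The printed value therefore fits neither 680 nor the 2021 total. It is about 11 times too small at 680 (0.541/0.05) and about 4 times too small at the 2021 total (0.20/0.05).

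**Step 4: co-exposure strata, zero events.** 1 - 0.025^(1/n) gives 0.75% at n = 490, 5.1% at n = 71 and 70.8% at n = 3.

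**The case against.** The best defence is that the study is descriptive. It has no hypothesis, power claim or target size, and Table 3 only assumes various event counts at a declared N. A reader might infer from the caption that the study is sized at 680. Section 8.5 does not say that; it leaves size to uptake and reports the current counts. A reader might also infer that every interval in the table is wrong. That does not follow either, because the rows with events are right for the N in the caption. These points stand, but they do not explain why intervals said to apply to the primary variables rest on a number that fits no count in the section.

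It could be said that 680 suits an earlier year. The protocol gives no counts for 2018-2020 and does not make that link, so this cannot be confirmed.

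It could also be said that the mismatch is harmless because it is conservative. At a fixed event count, a larger N scales the estimate and both limits together; for 5 events the upper-to-lower ratio is about 7 at either N, and only the absolute width shrinks. For rows with events the direction is indeed conservative. For the zero-event row it is not: the printed limit claims more precision than either N supports.

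Finally, Table 3 is for the primary variables, precision by stratum can be left to an analysis plan, and the count of 3 aPCC patients is printed directly above the table. The absence of stratum columns is therefore not an error.

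**Conclusion.** The point holds as an internal inconsistency plus one wrong table entry. Table 3 does not describe the population that the same section reports. For a given event count its non-zero rows are 2.66 to 2.77 times too high for 2021, and its zero-event upper limit of 0.05% is wrong at its own N (0.54%) and at the 2021 total (about 0.20%).

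This rests on two assumptions: that the alone group is defined as in Section 8.3.2, and that the table is meant to inform the annual analyses of all exposed patients. Section 8.5 does not tie it to a year. If the first assumption failed, the 1,319 patients in the alone group would still be 1.94 times 680.

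A reader might conclude that the table understates precision throughout. The zero-event row contradicts that. The conduct of the study is unaffected, but the protocol's only precision statement should be corrected.

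**What to change.** Recalculate Table 3 on the de-duplicated current annual exposed total from the EUHASS report, or on a stated range of N that includes it. A range is the more durable choice, because uptake varies and data collection now runs to the end of 2024. State where N comes from, whether the co-exposed groups overlap, and how Obizur users are counted. Correct the zero-event upper limit whichever N is kept.

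Optionally, add one line with the zero-event upper limits for the co-exposure groups (n = 490: 0.75%; n = 71: 5.1%; n = 3: 70.8%). Full columns would not work, since a group of 3 cannot hold 5 to 50 events.

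The cost is one recalculated table and a sentence or two of text, with no change to data or design.

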# 8.6 DATA MANAGEMENT

Treating centers transmit information regarding observed adverse events via the EUHASS website. Data is anonymized using a Soundex coding system derived by the reporting center; it is not possible to identify the patient from the information transmitted to EUHASS. No data audit is performed at the centers.

Individual level data related to adverse events are processed, analyzed, and summarized by EUHASS. Roche, as the MAH, receives the aggregate information in the form of annual emicizumab-specific annual reports. These annual reports may include selected information on individual adverse events. No other patient-level data are received by the MAH.

#### 8.7 DATA ANALYSIS

Descriptive statistics on endpoints, including number and percentage of patients, will be provided. Continuous variables will be summarized by mean, median, minimum, maximum, and IQR. Categorical variables will be summarized by counts, percentages, and corresponding 95% CIs. Data generated within the first 7 calendar years post-marketing authorization (2018–2024) are analyzed annually. Proportions of each adverse event, along with corresponding 95% CIs, may be calculated annually for all patients exposed to emicizumab if relevant. In addition, proportion of TE and TMA may be calculated annually for patients exposed to emicizumab and each of the following agents: aPCC, rFVII, and FVIII if relevant.

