## **DATA ANALYSIS**

Data generated within the first 7 calendar years post-marketing authorization (2018–2024) are analyzed annually. Proportions of each adverse event, along with corresponding 95% confidence intervals, may be calculated annually for all patients exposed to emicizumab if relevant. In addition, the proportion of TE and TMA may be calculated annually for patients exposed to emicizumab and each of the following agents: aPCC, rFVII, and FVIII if relevant.

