#### 7.2 OBJECTIVES

The primary objective for this study is as follows:

 To estimate the incidence of TE, TMA, and anaphylaxis in patients exposed to emicizumab, with or without coagulation factor products

The secondary objectives for this study are as follows:

- To estimate the incidence of TE and TMA in patients exposed to emicizumab alone and concomitantly with each of the following drugs: aPCC, rFVIIa, and FVIII product
- To describe individual cases of TE and TMA based on available information
- To summarize the frequency of other adverse events collected by EUHASS in patients exposed to emicizumab
- To describe individual cases of "unexpected poor efficacy" reported to EUHASS based on the available information

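### Section 8.7 plans only calendar-year proportions, words them both as optional and as firm, and names no cumulative 2018–2024 estimate

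*Protocol*

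**What the plan says.** The primary objective in Section 7.2 is "To estimate the incidence of TE, TMA, and anaphylaxis in patients exposed to emicizumab, with or without coagulation factor products". Section 8.7 sets the analysis frame: "Data generated within the first 7 calendar years post-marketing authorization (2018–2024) are analyzed annually". For the estimate itself it says: "Proportions of each adverse event, along with corresponding 95% CIs, may be calculated annually for all patients exposed to emicizumab if relevant". The synopsis, under Data Analysis, uses the same conditional form ("may be calculated annually for all patients exposed to emicizumab if relevant"). The next sentence of Section 8.7 treats TE and TMA by co-administered drug in the same way and mentions no interval.

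Other text is firmer. Section 8.7 opens by committing to counts, percentages and 95% CIs for categorical variables. Section 6 says the registry reports will be used to calculate incidence, and Section 8.9 says the co-exposure counts are used to calculate annual incidence. Section 8.1 lists, without condition, the yearly number exposed and the number with each event; only the derived proportion is qualified by relevance.

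No section describes a pooled or cumulative estimate. Section 5 gives the final report a date, and Section 10 says events will be summarized in it, but neither says that the years are combined. On size, Section 8.5 gives counts for 2021 only: "1,319 patients were treated with emicizumab alone, 71 patients were treated with emicizumab and NovoSeven", 490 with FVIII, and "3 patients were treated with emicizumab and Factor Eight inhibitor bypassing activity (FEIBA".

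**The concern.** The events are rare and the aim is to estimate how rare. For such events precision comes from accumulating exposure, and Amendment 4 extends the study to the end of 2024. An analysis that stays within calendar years gains no precision from the added years: each new year is one more estimate with its own wide interval.

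The aPCC group matters most. Sections 3 and 6 tie both identified risks, TE and TMA, to aPCC use with emicizumab, and it is by far the smallest group. In a single year of 2021 size its proportion cannot be interpreted.

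The mixed wording adds a second problem. Relevance is not defined, so the text leaves open whether a year with no events gets a proportion and an interval. In such a year the upper limit is the informative result.

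**Working it through.** **Inputs, all from the protocol.** Section 8.5, calendar year 2021: emicizumab alone 1,319; with rFVIIa (NovoSeven) 71; with FVIII other than Obizur 490; with aPCC (FEIBA) 3. Section 8.7: seven calendar years. Table 3: two-sided 95% exact binomial intervals, "Based on 680 Patients Receiving Emicizumab".

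**Formulas.** With zero events in n, the exact (Clopper–Pearson) upper limit is 1 − 0.025^(1/n). Treated as a Poisson rate over N, it is −ln(0.025)/N = 3.689/N.

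**The plan's own figures.** The Table 3 intervals for 1, 5, 10, 20 and 50 events reproduce; for example, 5/680 gives 0.24–1.71% and 20/680 gives 1.81–4.51%. The zero row does not: 1 − 0.025^(1/680) = 0.54%, where the table prints 0.05%. A limit of 0.05% would need ln(0.025)/ln(0.9995), about 7,376 patients. This looks like a slipped decimal and is a separate error from the present point, though it falls in the row that applies to a zero-event year.

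**One year against seven, zero events.** Only 2021 is given, so the pooled columns assume that every year equals 2021.

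| Group | n, 2021 | Upper limit, 0/n | 7 × n | Upper limit, pooled |
|---|---|---|---|---|
| With aPCC | 3 | 70.8% | 21 | 16.1% (Poisson 3.689/21 = 17.6%) |
| With rFVIIa | 71 | 5.1% | 497 | 0.74% |
| With FVIII | 490 | 0.75% | 3,430 | 0.11% |
| Emicizumab alone | 1,319 | 0.28% | 9,233 | 0.04% |
| All emicizumab | 1,883 | 0.20% | 13,181 | 0.03% |

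The last row is 1,319 + 71 + 490 + 3 and assumes that the four groups do not overlap. If every rFVIIa and aPCC patient also received FVIII, the total would be 1,319 + 490 = 1,809, and the one-year limit would still be 0.20%.

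**Sensitivity for aPCC.** If the seven-year total were 10, the zero-event limit would be 30.8%; if 50, 7.1%. With one event, 1/3 gives 0.8–90.6% and 1/21 gives 0.1–23.8%.

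**With events.** At one event a year among all emicizumab patients, the interval width falls from 0.29 percentage points (1/1,883) to 0.09 (7/13,181).

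**The case against.** The strongest reply has four parts.

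First, a reader might infer that the incidence estimate is wholly optional. The text does not support that: Section 8.7 also promises percentages with 95% CIs, and Sections 6 and 8.9 speak of incidence being calculated. What stands is a conflict between conditional and firm wording.

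Second, a reader might infer that proportions will be shown only for years with events, which would bias the published set upward. The documents do not say so. Yearly numerators and denominators are reported unconditionally, so a zero-event year still shows its zero and its denominator, and anyone can compute the interval. Any figure for the size of such a bias would need an invented event rate and a meaning of relevance that the protocol does not state.

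Third, annual analysis follows the periodic safety reporting cycle and does not forbid a cumulative table, which a SAP may specify. The SAP is not shown, so the absence can be asserted for the protocol only. That weakens the point but does not remove it, because Section 8.7 positively fixes the year as the unit of analysis and Section 8.7.1 says the data are analyzed according to this protocol.

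Fourth, pooling has limits of its own. The registry counts patients with any use in a calendar year and describes no exposure duration. The sponsor receives aggregate reports, so repeat patients cannot be removed. Section 6 shows that the indication widened during the study. All of this is correct and shapes the fix.

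**Conclusion.** The point holds as a recommended improvement. The protocol specifies only calendar-year proportions, gives them conflicting status, and names no cumulative estimate, so the primary objective gains no precision from the years that Amendment 4 adds.

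Under the constant-2021 assumption, pooling would tighten the zero-event limit about sevenfold in the larger groups and from 70.8% to about 16–18% for aPCC. Two stronger readings should be resisted:

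- Three aPCC patients is the 2021 count. The protocol does not give it as a yearly figure.
- The yearly results are not uninformative throughout. One 2021-size year with no events already bounds the risk at about 0.2–0.3% for all emicizumab patients or emicizumab alone. The precision problem is severe for aPCC and milder for rFVIIa.

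No data are lost under the present plan, because counts are reported every year and can still be combined at the end. That is why this falls short of an essential correction.

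**What to change.** In Section 8.7 and the synopsis, reconcile the wording: proportions with exact 95% CIs will be calculated for every year, including years with no events. Carry the same change into the report contents listed in Section 8.1 and in the synopsis.

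Add a cumulative 2018–2024 estimate to the final report: total patients with an event over the sum of the annual patient counts, with an exact 95% CI of a named type (exact binomial would match Table 3). Give it for all emicizumab, for emicizumab alone, and for each co-exposure group. Emicizumab alone is in the secondary objective but is not listed in the co-exposure sentence of Section 8.7.

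Label the unit as patient-calendar-years of any use. It is neither person-time nor a per-person cumulative risk. State that patients recur across years, that the interval treats their years as independent, and that Year 1 covers only April to December 2018. Keep the yearly rows beside the pooled row.

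The cost is a few sentences and one table from reports the sponsor receives anyway, with no new data collection. The drawback is that pooling averages over a changing case mix. The aPCC estimate also stays imprecise when pooled, so it should be read with the case descriptions.

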# 8.7.1 Analyses Timelines

Emicizumab-specific annual reports are expected to be received from EUHASS 12–14 months following the end of each calendar year (e.g., 2018 report is expected between December 2019 and February 2020). Based on this, the Sponsor will analyze the data according to this protocol within 4 months. The results of the analyses will be

provided to European Medicines Agency (EMA) via the next periodic safety update report (PSUR)/periodic benefit-risk evaluation report (PBRER).

### 8.8 DATA QUALITY ASSURANCE AND QUALITY CONTROL

The MAH must maintain adequate and accurate records to enable the conduct of the study to be fully documented, including but not limited to the protocol and protocol amendments. EUHASS standard operating procedures, internal policies and process guidance, and/or routine guidance will be used for data collection, which is performed independent of the MAH and this PASS. These procedures may include, among others, rules for data storage, methods to maintain and archive study documents, and quality-control procedures. Although EUHASS follows up and confirms the accuracy of each adverse event reported, no systematic site audits are performed. EUHASS is responsible (outside of this study) to obtain and maintain Informed Consent Forms (if applicable) and documentation of Institutional Review Board (IRB)/Ethics Committee from the participating centers.

